## ***Six Month Follow-up Form***

---

If the patient is still in hospital when the six month follow-up is due, the randomising clinician will be sent a hospital version of the six month follow-up form which should be completed with the patient (Appendix E).

For those patients who have been discharged, outcome will be assessed blindly via a postal (or telephone if post not possible) questionnaire (Appendix D). This will be sent to the patient directly from the FOOD Trial Co-ordinating Centre or via the National Co-ordinators (for non-UK centres). The questionnaire will establish their:

- Type of residence (own home, with relatives, residential or nursing home)[as a guide to resource use]
- Functional status - degree of functional impairment on the Modified Rankin Scale,
- 'Simple questions', and Health Related Quality of Life (HRQoL) measured using EUROQoL.
- Feeding status - whether they are now feeding normally or still have a feeding tube in place.

Prior to the six month follow-up, their family doctor will be contacted by post or phone to establish the patient's:

- Current address (to allow follow-up).
- Date of death (if applicable).

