## Randomisation Procedure

Data, collected at baseline, will include centre identifiers, patient identifiers and information which will provide a prediction of outcome (e.g. is the patient able to lift both arms off the bed?). Data required to allow minimisation (see below) and to calculate the delay from stroke onset to hospital admission and randomisation will also be collected. A swallowing assessment, carried out by the randomising clinician or a member of his/her team, will determine which trial(s) the patient can be entered into. The swallowing assessment should be performed in line with local guidelines, but as a minimum should comprise a bedside assessment.

To randomise, the clinician completes the randomisation form (Appendix A) by answering questions relating to the patient's ability to take adequate fluids orally and their uncertainty about the best feeding policy. We have adopted a randomisation algorithm (see below) to ensure that patients enter the trial (or trials) which best addresses the responsible clinicians' uncertainties. The clinician then telephones the 24 hour randomisation service using a freephone number. At the end of the call, the operator (or system) will inform the clinician of the allocated treatment regimen which the clinician should note on the randomisation form and then ensure that the allocation is given. The randomisation form should then be faxed immediately to the FOOD Trial Co-ordinating Centre.

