## ***Hospital Discharge Form***

---

At discharge, transfer from the randomising centre or death, the randomising clinician, or the trial support staff in that centre will review the case notes and drug charts, complete a Hospital Discharge Form (Appendix C) and return it to the FOOD Trial Co-ordinating Centre in Edinburgh.

Clinicians who routinely transfer their patients with stroke to another ward/unit/hospital very soon after admission will need to reach an agreement with that ward/unit/hospital such that the allocated feeding regimen will be continued and that the Hospital Discharge Form will be completed on discharge, death or transfer from that ward/unit/hospital.

The data collected will be used to:

- Determine what nutritional support the patient actually received during hospital admission.
- Provide contact data to allow six month follow-up to be organised centrally.
- Provide data concerning early outcome and use of hospital facilities.
- Provide data relating to any adverse events and complications of the feeding regime.

These data should be available from the medical or nursing notes.

If a Hospital Discharge Form has not been received by the Food Trial Co-ordinating Centre before the six months follow-up is due, the FOOD Trial Co-ordinating Centre in Edinburgh will contact the randomising clinician to confirm the patient's whereabouts. If the patient is still in hospital, a hospital version of the Follow-up Form (Appendix E) will be sent to the clinician for completion. The Hospital Discharge Form should then be completed on eventual discharge, transfer from the randomising centre or death.

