**Thank you very much for taking the time to complete this form. Please return it using the pre-paid envelope provided**

## The International Stroke Trials Collaboration (Feed Or Ordinary Diet)

Doctors questionnaire – patient still in hospital at 6 months

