**Who is responsible for their daily care (if this is NOT you)**

**Please complete this form by asking the following questions.**

In the next section we would like your patient to read the following descriptions and choose the one which best describes their present state. If your patient cannot read or complete the questionnaire, please complete it on their behalf.

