### EXAMPLE

Following the example on the right we would like you to indicate on this scale how good or bad your health is today, in your opinion. Please do this by drawing a line from the box 'Your own health today' to whichever point on the scale indicates how good or bad your current state is.

Your own health state today

Are these responses?

The patients  The doctors

Name of person completing the form:

Date:

(Please PRINT clearly)

day  month  year

**Thank you very much for taking the time to complete this form.  
Please return it using the pre-paid envelope provided**

FOOD/FU6/1/898

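### For patients still in hospital at six months, the primary-outcome Rankin score is collected through the unblinded randomising clinician, so the mode of assessment depends on a state that feeding policy may alter

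*Protocol*

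**What the plan says.** The protocol's Six Month Follow-up Form section sets up two routes to the primary outcome.

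- **Discharged patients:** "For those patients who have been discharged, outcome will be assessed blindly via a postal (or telephone if post not possible) questionnaire". It is sent by the co-ordinating centre or, outside the UK, through the National Co-ordinators.
- **Patients still in hospital:** "the randomising clinician will be sent a hospital version of the six month follow-up form which should be completed with the patient". The Hospital Discharge Form section gives the same routing: "a hospital version of the Follow-up Form (Appendix E) will be sent to the clinician for completion".

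The hospital version (Appendix E) is headed "Doctors questionnaire – patient still in hospital at 6 months". The patient is meant to read the Rankin descriptions and choose one, but the doctor is told: "If your patient cannot read or complete the questionnaire, please complete it on their behalf". A box at the end ("Are these responses") records whether the answers are the patient's or the doctor's.

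The randomising clinician is not blind. Under Randomisation Procedure, "the operator (or system) will inform the clinician of the allocated treatment regimen", and the clinician must then see that it is delivered. The Primary Outcomes section uses Rankin below 3 for Trial 1 and below 4 for Trials 2 and 3, both at six months after first randomisation.

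**The concern.** Two features combine.

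First, for inpatients the person who handles the form, and who rates the patient when the patient cannot respond, knows the allocation. Under Duration of Feeding Regimen, the clinician may also have changed the feeding method after becoming convinced that another was better. The protocol provides no independent or blinded assessor for this group.

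Second, the route is chosen by a post-randomisation state. The Secondary Questions ask whether feeding policy affects use of hospital facilities and final placement, and the Secondary Outcomes include time to discharge and length of stay. If feeding policy changes who is still in hospital, the share of outcomes collected through the clinician will differ between arms.

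The cut for Trials 2 and 3 separates needing some help in looking after oneself from needing other people's help without round-the-clock attention. That is a matter of judgement. Any arm-dependent rating there adds directly to the estimated treatment difference, and a larger sample does not remove it. An analysis plan can examine the effect but cannot change how the data were collected.

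**Working it through.** **1. The plan's own figures.** The protocol claims at least 80% power in each trial at alpha 0.05. With a two-sided normal approximation (pooled variance under the null) and equal groups:

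| Trial | N | Rates | Power |
|---|---|---|---|
| 1 | 6000 | 52% vs 56% | 87.5% |
| 2 | 2000 | 30% vs 36% | 81.5% |
| 3 | 1000 | 30% vs 39% | 85.0% |

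The claim is met throughout. This point disputes no figure in the plan and alters no sample size.

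**2. Bias model.** Let h be the share of all randomised patients still in hospital at six months. Let m be the net shift in the proportion rated as a good outcome among them, in one arm relative to the other. Then bias = h × m. Neither h nor m is in the protocol; both ranges below are assumptions.

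- Low end: 2% × 5 points = 0.1 points.
- Middle: 5% × 10 points = 0.5 points.
- Higher: 10% × 10 points = 1.0 point.
- High end: 10% × 20 points = 2.0 points.

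As a share of the target difference, 0.1 to 2.0 points is 1.7% to 33% of 6 points (Trial 2), 1.1% to 22% of 9 points (Trial 3), and 2.5% to 50% of 4 points (Trial 1, if the same m applied there).

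**3. Effect on type I error.** With no true effect, SE = √(2p(1−p)/n), with p the control rate and n the number per arm:

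- Trial 1: √(2 × 0.52 × 0.48 / 3000) = 0.0129
- Trial 2: √(2 × 0.30 × 0.70 / 1000) = 0.0205
- Trial 3: √(2 × 0.30 × 0.70 / 500) = 0.0290

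Rejection probability = Φ(−1.96 + bias/SE) + Φ(−1.96 − bias/SE):

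| Bias | Trial 2 | Trial 3 | Trial 1 (same m) |
|---|---|---|---|
| 0.5 points | 5.7% | 5.3% | 6.7% |
| 1.0 point | 7.8% | 6.4% | 12.1% |
| 2.0 points | 16.4% | 10.6% | 34.1% |

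The Trial 1 column is higher only because that trial is larger. It should not be read as an expectation, because the same m is unlikely there. The Trial 1 cut lies between Rankin 2 (still able to look after oneself) and Rankin 3, and a patient in hospital six months on is unlikely to be near it.

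**4. Route alone.** Bias can arise even if clinicians rate both arms alike. Suppose clinician collection shifts ratings by 10 points relative to central collection in both arms, but h is 5% in one arm and 10% in the other (all assumed). The bias is then (10% − 5%) × 10 points = 0.5 points.

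**The case against.** The strongest reply is that this is a reasonable choice in favour of complete data. The hospital form is to be filled in with the patient, and the doctor answers only if the patient cannot. Some of the most disabled patients cannot manage a postal or telephone questionnaire, and the Consent section recognises that some have no close relative. A missing primary outcome in such patients could do more harm than a bias of a point or less. The source of the answers is recorded, so a sensitivity analysis is already possible. Entry requires substantial uncertainty about feeding, which makes a consistent one-way shift across many centres less plausible. The randomising clinician may also no longer be giving daily care, as Appendix E itself allows.

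Much of this stands. It is why the size is modest and why clinician completion should not be abolished. It does not explain why the treating side should be the first route rather than the last. Recording the respondent allows bias to be examined but does not prevent it.

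Three stronger readings are tempting but unsupported:

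- **That clinicians will often rate these patients, or commonly do so in Trials 2 and 3.** The protocol makes this conditional on the patient being unable to respond and gives no frequency.
- **That type I error is inflated by a known amount.** Every such figure above rests on assumed h and m.
- **That the description of discharged patients' assessment as blinded is itself a material error.** Patients and relatives plainly know how the patient was fed, so only central handling can be blind, but rewording the sentence would change no result.

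**Conclusion.** The point holds in a limited form. For an unquantified minority of patients, the protocol routes the primary-outcome Rankin item to a clinician who knows the allocation and who supplies the answer when the patient cannot. Survivors who have been discharged are assessed centrally. Which route applies is settled after randomisation and may depend on feeding policy.

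Under the assumed ranges (h 2–10%, m 5–20 points) the bias is 0.1–2.0 points. The upper end needs both extremes together. In the middle case of 0.5 points, type I error stays close to nominal in Trials 2 and 3. The bias shrinks further if nearly all inpatients are clearly Rankin 4 or 5, and classification of deaths is unaffected. The concern is mainly for Trials 2 and 3; for Trial 1 it is probably small. It justifies a cheap improvement to data collection and does not threaten the design.

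**What to change.** Amend the Hospital Discharge Form and Six Month Follow-up Form sections and Appendix E as follows.

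1. The clinician confirms where the patient is, as already planned.
2. The co-ordinating centre or National Co-ordinator then obtains the Rankin and EuroQoL answers directly from the inpatient or a relative, by the existing post or telephone route. It uses the Appendix D questions with a hospital option added to the residence item, which at present offers only own or relative's home, residential home and nursing home.
3. Clinician completion remains a last resort when neither patient nor relative can respond, flagged by the existing respondent box.
4. A sensitivity analysis of the primary outcome examines doctor-rated responses by arm.

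**Cost:** changes to wording and forms, some extra chasing, and more proxy answers from relatives. No sample size changes. Because patients and relatives also know the regimen, the change removes rating by the treating clinician wherever another respondent exists and aligns the mode of assessment. It does not achieve full blinding.

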# ANALYSES

---

All analyses will be based on intention-to-treat.

## ***Primary Outcomes***

---

The primary outcome for Trial 1 will be the proportion of patients who are surviving free of dependency (defined as a Modified Rankin <3) six months after first randomisation.

The primary outcome for Trials 2 and 3 will be the proportion of patients surviving free of severe disability (defined as a Modified Rankin <4) six months after first randomisation.

## ***Secondary Outcomes***

---

- Proportion of patients who are dead at one and six months.
- HRQoL amongst survivors.
- Time to hospital discharge.
- Length of stay in hospital which will provide a surrogate outcome for analysis of cost.
- Number of days of tube feeding.
- Adverse effects of feeding regimes.
- Premature cessation of feeding regimes and reasons.

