## ***Duration of Feeding Regimen***

---

The oral supplements (Trial 1) should normally be continued until hospital discharge. However, the responsible clinician may choose to stop supplements earlier if, for example, the patient is gaining excessive weight. Tube feeding should continue until the responsible clinician decides that the patient is taking adequate diet orally or that further tube feeding is futile. The reason for stopping the feeding regime should be recorded on the Hospital Discharge Form (Appendix C). This form should be completed on discharge from hospital, death or transfer out of the randomising centre, although the allocated feeding policy can be continued after discharge or transfer, if appropriate. Details of **all** types of feeding given since randomisation should be recorded on the Hospital Discharge Form (Appendix C), including those feeding regimens not randomly allocated.

If the patient has been randomised to one feeding policy but this subsequently becomes impractical or the clinician becomes certain that an alternative is better then the clinician may change the method of feeding, although our analyses will be based on intention-to-treat. Data on how often, and why, feeding policies are changed will inform our final analyses.

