## The International Stroke Trials Collaboration (Feed Or Ordinary Diet)

### Hospital Discharge Form

**PLEASE COMPLETE THIS FORM ON THE PATIENT'S DISCHARGE FROM HOSPITAL, TRANSFER FROM THE CENTRE OR DEATH (whichever occurs first) AS ACCURATELY AS POSSIBLE**

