## PART 3 Fed via another type of tube (e.g. PEG) SINCE Randomisation (Please enter 99/99/99 or 99 if unknown)

Type of tube inserted  Gastric       Duodenal/jejunal

Method of insertion  Endoscopic       Radiological guidance

Date first tube inserted after randomisation: day   month   year

Number of tubes inserted SINCE randomisation:

Is the tube still in situ? YES  NO

If NO, date last tube removed: day   month   year

Name(s) of feed given: \_\_\_\_\_

Did PEG tube deliver satisfactory volumes of liquid feed? YES  NO  Uncertain

If PEG feeding stopped, please indicate the primary reason below (please tick (✓) one box only)

- Patient taking adequate diet and fluids orally
  - Patient discharged/died
  - Difficulties encountered (please specify difficulties below)
  - Other (e.g. feeding futile), please specify: \_\_\_\_\_
- For office use

Were any difficulties experienced? (please tick (✓) one or more boxes)

- No
  - Difficulties with tube insertion
  - Wound infection
  - Haemorrhage from PEG site
  - Other, please specify: \_\_\_\_\_
  - Patient pulled out the tube(s)
  - Aspiration
  - Peritonitis
- For office use

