## The International Stroke Trials Collaboration (Feed Or Ordinary Diet)

### FOLLOW-UP QUESTIONNAIRE

#### CONFIDENTIAL

Dear

On:

you were admitted to:

under the care of:

and, we would like to know how you are now. We need to know what you are **actually managing** to do now, not what you used to do, or would like to do.

Please tick (✓) one box on each line

	YES	NO
Has the stroke left you with any problems?		
Do you need help from anybody with everyday activities?		

**How do you live now?** (please tick (✓) **ONE** box only)

On my own		
With my partner or relatives		

**Where do you live now?** (please tick (✓) **ONE** box only)

In my own home or my relative's home		
In a residential home		
In a nursing home		

In the next section we would like you to read the following descriptions from people who have had similar medical problems to you and choose the one which best describes your present state.

Tick the **ONE** box next to the sentence which best describes your present state.

- I have no symptoms at all
- I have a few symptoms but these do not interfere with my everyday life
- I have symptoms which have caused some changes in my life but I am still able to look after myself
- I have symptoms which have significantly changed my life and I need some help in looking after myself
- I have quite severe symptoms which mean I need to have help from other people but I am not so bad as to need attention day and night
- I have major symptoms which severely handicap me and I need constant attention day and night

We would also like to know how you are **NOW** being fed

- I now consider that I can eat normally
- I am fed via a tube in my nose
- I am fed via a tube in my side

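### Length of stay and time to discharge are cut short for patients transferred to another hospital, and tube days for patients who leave with a tube in place, because no later contact collects the missing dates

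*Protocol*

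**What the plan says.** The protocol's Secondary Outcomes section lists "Time to hospital discharge", "Length of stay in hospital which will provide a surrogate outcome for analysis of cost" and "Number of days of tube feeding". None of the three is restricted there to the randomising centre, and tube days have no stated time window.

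The dates come from the Hospital Discharge Form (Appendix C). The Follow-up section fixes when it is filled in: "At discharge, transfer from the randomising centre or death, the randomising clinician, or the trial support staff in that centre will review the case notes". The form's own instruction agrees: "TRANSFER FROM THE CENTRE OR DEATH (whichever occurs first").

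Part 6 lists another hospital among the discharge destinations, next to home and care home, with one discharge date for all of them. Parts 2 and 3 ask for a tube-removal date only if the tube is already out; the Part 3 question is "Is the tube still in situ". Yet the section on duration of the feeding regimen says that "the allocated feeding policy can be continued after discharge or transfer, if appropriate".

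At six months, Appendix D asks about current residence and current feeding, with options such as "I am fed via a tube in my side". Appendix E asks whether a tube is in place and where the patient is. The family doctor is asked for an address and any date of death. None of these contacts asks for a final discharge date or a tube-removal date.

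**The concern.** Total hospital stay and total tube days need end dates that, for some patients, fall after the only dated form has closed. An analysis plan cannot recover a date that was never collected.

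The third secondary question asks about use of hospital facilities, and stay is offered as a stand-in for cost. If transferred patients go on to a substantial second stay, average use is understated. If one feeding policy also leads to more or earlier transfers, a shorter recorded stay could reflect the move and not a real saving. Tube days carry the same risk in the PEG versus NG comparison, because the protocol expressly allows feeding to continue after the patient leaves.

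**Working it through.** The protocol gives no transfer rate, standard deviation or target difference for these outcomes, so there is no stated figure to reproduce. The check has two parts.

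**1. Which patients have complete data**

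| Patient's course | Stay and time to discharge | Tube days |
|---|---|---|
| Discharged directly home or to a care home, tube out | Complete | Complete |
| Discharged directly home or to a care home, tube in place | Complete | Truncated at discharge |
| Died in the centre | Complete to death | Complete |
| Transferred to another hospital, tube out | Truncated at transfer | Complete, unless tube feeding restarts |
| Transferred to another hospital, tube in place | Truncated at transfer | Truncated at transfer |

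Two provisions in the Follow-up section narrow the gap:

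- Centres that routinely move patients very early must agree with the receiving unit that it completes the form. That moves the closing point to the receiving unit, but the form still closes at the next transfer.
- If no form has arrived by the time six-month follow-up is due and the patient is still in hospital, the form is completed later. A form already returned at transfer is outside this provision.

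**2. Possible size, under assumed values**

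Let p be the proportion affected in an arm and D the mean unseen days per affected patient.

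- Understatement of the arm mean = p × D
- Spurious difference between arms A and B = p_A × D_A − p_B × D_B

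*Level of stay.* Assume that 10% to 40% are transferred with 20 to 60 unseen days:

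- low: 0.10 × 20 = 2 days
- central: 0.25 × 40 = 10 days
- high: 0.40 × 60 = 24 days

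*Difference in stay between arms when there is no true difference:*

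- same transfer rate and same unseen days, for example 20% and 30 days in both arms: 6 − 6 = 0 days
- transfer rates 10 points apart, same unseen days: 0.10 × 20 = 2 days to 0.10 × 60 = 6 days
- same rate of 25%, unseen days of 40 and 60: 0.25 × 60 − 0.25 × 40 = 15 − 10 = 5 days

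*Difference in tube days between arms when there is no true difference:*

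- 10% versus 20% leaving with a tube, 30 to 90 later tube days: 0.10 × 30 = 3 to 0.10 × 90 = 9 days
- 10% versus 40%: 0.30 × 30 = 9 to 0.30 × 90 = 27 days
- equal shares and equal later days: 0 days

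In each case the arm with more unseen time looks shorter than it is.

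**The case against.** The strongest reply has four parts.

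- **Most records may be complete, and the incomplete ones are visible.** For a patient going home or to a care home, form closure is the discharge itself. A transferred patient is marked as gone to another hospital, and a tube in place is flagged. It is tempting to infer that these outcomes cannot be measured at all, or that a patient moved on day 20 is recorded as having a finished 20-day stay. Neither holds: the destination is recorded with the date, so the observation can be censored.
- **Censoring rules and time windows normally belong in the analysis plan**, which is not shown. That is fair for the rules. But censoring at transfer assumes that transfer is unrelated to the remaining stay, which is hard to defend, and it does not yield total stay. The six-month tube question helps only in part. If the tube is gone by then, removal is known only to lie between form closure and the six-month contact.
- **The form's stated purpose is in-hospital care and early outcome.** That supports a centre-limited reading, but the outcome list does not state one, and the cost claim needs total stay.
- **Bias between arms is conjecture.** This stands. No passage says that transfer or discharge timing differs by arm. The Background makes a difference plausible for Trial 3, since NG tubes are described as often pulled out and as causing ulceration with prolonged use, and many clinicians are said to keep PEG for expected long-term feeding. It remains an inference.

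It is also true that only secondary outcomes are touched, that placement is captured at six months, and that limited data collection suits large, simple trials.

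**Conclusion.** The point holds as a gap in data capture for two identifiable groups: patients transferred to another hospital (stay and time to discharge) and patients who leave with a tube in place (tube days). The gap is clearest for tube days, because it affects everyone leaving with a tube, wherever they go.

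The mean level of stay is understated by p × D, which is 2 to 24 days over the assumed ranges. A reader might go further and conclude that the arm comparisons are biased. The documents do not support that. Bias arises only if the proportions affected or the unseen days differ by allocation, and the protocol gives no information on either. Every figure in days rests on assumed rates and durations.

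The six-month primary outcomes are unaffected. The change is worth making because it is cheap and because the dates are hard to recover afterwards, but it does not threaten the main conclusions of the three trials.

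**What to change.** For patients recorded as transferred to another hospital, or as leaving with a tube in place, collect two dates at contacts already planned:

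- **Family-doctor contact and Appendix D:** date of final discharge from hospital, and date of tube removal if it has been removed.
- **Appendix E:** date of tube removal only. These patients are still in hospital, so a final discharge date does not apply; stay is censored at six months.

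Then define stay as days in any hospital, and tube days as running to removal, death or six months.

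The cost is two extra questions for a subset of patients. The downside is recall error and some missing dates, particularly from postal replies by patients or relatives.

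If the dates are not collected, make three changes instead: restate the outcomes as stay in the randomising centre and tube days up to leaving it; treat transfers to another hospital as censored, not as discharges; and do not present stay as a surrogate for total hospital cost. This alternative costs only wording, but it gives up the wider question of hospital use for transferred patients.
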